2.1 Introduction

Adolescents are disproportionately affected by sexually transmitted infections (STIs)¹⁻³ and account for 9 million of the 19 million new STI cases annually.² The STI epidemic among youth is a national public health priority as noted in the Healthy People 2020 objectives, which specifically recommend enhanced STI diagnosis, treatment, and reduction in adolescents.⁴ Failure to diagnose and treat STIs in a timely manner results in serious reproductive morbidity, mortality, and increased transmission of disease.

Adolescents frequently access the emergency department (ED) for care,⁵⁻¹⁰ with the ED functioning as the primary source of health care for over 1.5 million adolescents.^{9, 11, 12} EDs are potentially high-yield sites for the delivery of sexual health services as part of a larger public health prevention strategy. Although the Centers for Disease Control and Prevention recommend universal HIV screening in EDs,¹³ no recommendations currently exist for gonorrhea and chlamydia (GC/CT) screening; thus <1% of the ED population is screened for GC/CT.¹⁴ Addressing the effectiveness and integration of ED-based STI screening is critically needed.^{15, 16}

Insufficient knowledge of the ideal structure for delivery (i.e. universally-offered or targeted to high risk groups) is a barrier to the implementation of ED-based GC/CT screening. While universally-offered screening (offered to all, regardless of risk) may detect a larger number of cases than targeted screening (screening only those disclosing high risk sexual behavior), it is more resource-intensive and may result in more false positive cases due to a lower pretest probability of infection. The Co-PIs, Drs. [name] and [name], are NICHD K23-funded investigators who are well-positioned to address this knowledge gap. They each study targeted ([name]) and universally-offered ([name]) ED-based GC/CT screening via electronically entered patient-reported data providing real-time clinical decision support (CDS). They have shown that both strategies are acceptable, feasible, and result in increased STI screening rates at their respective pediatric EDs;¹⁷⁻²³ but it is unknown which method is most efficient and cost effective when instituted across a national sample of pediatric EDs with varying community STI prevalence.

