with targeted screening. To be complete, we also will include usual care as a third strategy. A simple model will only examine effectiveness in terms of STIs detected. A more complicated model will include short- and long-term consequences of treated and untreated disease. Short-term outcomes will include the likelihood of follow-up and treatment once a diagnosis has been made, along with the efficacy of antibiotic therapy. Based on test characteristics from the literature, small numbers of patients may have false positive or false negative test results. We will model the consequences of both, in terms of additional costs and consequences of unnecessary treatment for false positives, and the costs and consequences of undetected/untreated STI in the case of false negatives. Outcomes also will be modeled for unscreened patients who later return for treatment of symptomatic disease (e.g., acute pelvic inflammatory disease). Long-term outcomes addressing the sequelae of untreated/ undetected STIs (tubal infertility, ectopic pregnancy, and chronic pelvic pain) and outcomes following successful detection and treatment will be modeled. Data generated from Aim 2 regarding the effectiveness of the two screening strategies in detecting GC/CT, the proportion of identified patients who ultimately receive treatment, and the prevalence ranges of GC and CT in cohorts presenting for ED care at the 6 sites in our study, will be used to inform probabilities in the model. Literature-based estimates will inform other probabilistic events and costs of long-term STI sequelae in the model. Incremental cost-effectiveness ratios will be calculated to determine cost-effectiveness. The analysis will use a health care sector perspective³⁴ that includes medical costs borne by third-party payers and paid out-of-pocket by patients. These will include current and future costs related to both the intervention and downstream events related to treated or missed STIs. We will perform a series of deterministic sensitivity analyses to explore the impact of parameter uncertainty on results, and known population variations. A key parameter of interest is the background rate of STI. This likely varies from location-to-location, and will be a key determinant to the cost-effectiveness of the universally offered screening strategy. We will calculate the threshold of background STI prevalence above which universally offered screening becomes very cost-effective (i.e., an ICER <\$50,000/QALY). As a result, the cost-effectiveness of the universally offered screening strategy may vary from location to location in the study, and in real-world use of the screening tool. Understanding this threshold may help shape policy for optimal screening strategies in different locations and settings.

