As additional secondary outcomes, for patients who consent to SHS completion, we will perform multivariable logistic regression to identify demographic and behavioral factors associated with GC/CT testing consent and GC/CT positivity.

Specific Aim 2. To determine the most cost-effective approach for GC/CT detection (i.e. usual care, targeted screening, and universally-offered screening) in an adolescent ED population.

Cost-effectiveness analysis: Markov state transition models will be built using readily available software (Decision Maker, Boston, MA). Health states will include those that impact prognosis, cost and quality of life, such as asymptomatic and symptomatic infection with GC and/or CT, pelvic inflammatory disease, infertility, ectopic pregnancy, and chronic pelvic pain. Because the median ED LOS for an adolescent is 4.25 hours, and we have previously demonstrated no significant difference in LOS between patients who completed the SHS compared to those who did not,¹⁷ time to complete survey will not be entered into the model. Furthermore, during a 4-hour ED visit, there is ample time to collect a urine sample, and urine testing is often already requested for clinical care. Therefore, time to obtain samples will also not be included in the cost analysis. We will use a one-month cycle length and a life-long time horizon. Patients will move between health states over time depending upon events that occur in each one-month cycle of the simulation. Health states and events will have associated quality of life and costs. We will perform analyses first using base case estimates for all parameters. We will next perform deterministic sensitivity analyses, examining key parameters one, two, or three at a time, to explore the impact of uncertainty and to address other plausible scenarios, such as populations with lower or higher prevalence of STIs. We also will be able to test various cut points for the STI risk prediction tool, described in aim 2, to see if there is an optimal cut point that minimizes the incremental cost-effectiveness ratio, finding the best balance between sensitivity and specificity for the risk prediction tool. Finally, we will perform probabilistic sensitivity analyses, using second order Monte Carlo modeling, to generate cost-effectiveness acceptability curves, providing further insights into the proportion of the time that the winning strategy will be cost-effective.

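### The cost model drops sample-collection time for reasons that do not address staff labour, which may understate the universal-versus-targeted ICER

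*Combined protocol and SAP*

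**What the plan says.** Two exclusions stand in the cost-effectiveness part of Section 5.1, each with its own reason.

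- **Survey time.** After giving a median adolescent stay of 4.25 hours, the plan says "we have previously demonstrated no significant difference in LOS between patients who completed the SHS compared to those who did not", and so "time to complete survey will not be entered into the model".
- **Sample time.** The reason here is that "during a 4-hour ED visit, there is ample time to collect a urine sample, and urine testing is often already requested for clinical care". The conclusion follows: "Therefore, time to obtain samples will also not be included in the cost analysis".

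Section 3.5 sets the costing frame: "The analysis will use a health care sector perspective", covering medical costs paid by third-party payers and by patients out of pocket. It adds that these comprise "current and future costs related to both the intervention and downstream events related to treated or missed STIs". The same section plans to find the background prevalence above which universal screening has an ICER below $50,000/QALY.

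Section 2.1 says of universal screening that "it is more resource-intensive and may result in more false positive cases", and Section 2.2 says that testing more low-risk patients costs more. Sections 4 and 4.1 have participants complete the sexual health survey in both screening phases.

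**The concern.** Collecting a urine sample takes staff minutes whether or not the patient stays longer. Room within a 4-hour visit is an argument about the patient's time, not about labour. The second argument does bear on labour, since a sample already requested needs little extra work, but it covers only some tests and the plan does not give the share.

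The omitted cost scales with the number of tests, and that number is where the two strategies are expected to differ. If universal screening runs more tests and finds more cases, leaving out any positive per-test cost makes its ICER against targeted screening too low and the prevalence threshold too low. That tilts the result toward hypothesis 2b. For hypothesis 2a, that universal screening is not cost-effective overall, the tilt runs the other way: support for 2a would be conservative, but 2a could be wrongly rejected.

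The deterministic and probabilistic sensitivity analyses in Section 5.1 cannot recover the effect, because a cost that is not in the model cannot be varied. The planned search for the risk cut point that minimises the ICER is exposed too, since the cut point decides how many patients are tested.

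**Working it through.** **The plan's own figure.** Section 5.2 puts about one third of asymptomatic patients in the targeted group, with 10-14% positive: 1/3 × 10% = 3.3% and 1/3 × 14% = 4.7%. This reproduces the stated detection rate of approximately 3-5%. The documents give no ICER, cost per test or staff time, so the effect can be sized only over assumed ranges.

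**Inputs from Section 5.2.** 220 asymptomatic patients per site per two weeks; targeted share f = 1/3; detection differences d = 1% and 0.5%, taken here as universal minus targeted.

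**Assumptions, not in the documents.** 5-10 staff minutes per sample at $0.75-1.00 per minute, so labour per test c runs from 5 × $0.75 = $3.75 to 10 × $1.00 = $10. Uptake a_U (universal) and a_T (targeted) and the share s of tests with urine already ordered are also unknown.

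**Formula.** Extra tests per extra case = (a_U − f × a_T) / d. ICER shift per extra case = c × (1 − s) × that number.

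**Reference case** (a_U = a_T = 1, s = 0). Tests per site-period: 220 against 220/3 = 73, a ratio of 3.0.

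| d | Extra tests per extra case | Shift at $3.75 | Shift at $10 |
|---|---|---|---|
| 1% | (1 − 1/3)/0.01 = 66.7 | $250 | $667 |
| 0.5% | (1 − 1/3)/0.005 = 133.3 | $500 | $1,333 |

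**What reduces it** (d held at 1%):

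- *Urine already ordered, c = $10:* s = 0.5 gives 0.5 × $667 = $333; s = 0.8 gives 0.2 × $667 = $133.
- *More patients tested under targeted screening.* Section 4.1 recommends testing for every sexually active patient, not only those at high risk. At f = 0.5 there are 50 extra tests per extra case (test ratio 2.0); at f = 0.7 there are 30 (ratio 1.4).
- *Lower uptake.* At 80% in both, (0.80 − 0.267)/0.01 = 53.3. At 50% universal against 80% targeted, (0.50 − 0.267)/0.01 = 23.3. At 33% against 100%, the test counts are equal and the shift is zero.

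**Per QALY.** At c = $10, d = 1% and s = 0, an assumed 0.01 QALY per case gives $667/0.01 = about $66,700 per QALY, and 0.1 gives about $6,700. Against a $50,000 threshold the omission could be decisive or modest.

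**Survey time.** With the survey completed in both phases, the count is 220 against 220, so the universal-versus-targeted increment is 0.

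**The case against.** The strongest reply is that no bias is established. Section 3.5 counts payments by third-party payers and patients, and staff minutes that generate no separate payment are not clearly among them. The unit cost of a test may already contain collection, in which case adding minutes would double-count. Section 5.1 drops time, not the cost of tests, so the extra cost of testing low-risk patients can still enter through test prices. All of this stands, and it makes the bias conditional. It does not justify the exclusion, because the plan neither says what the unit cost contains nor rests its exclusion on that ground. For the same reason, a flat contradiction between Sections 3.5 and 5.1 would be too strong a reading.

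Four other readings are tempting and are not supported:

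- *That leaving out survey or tablet time also favours universal screening over targeted.* Both phases incur it, so it cancels. It matters only when either strategy is compared with usual care, the third strategy in Section 3.5.
- *That both exclusions rest on unchanged length of stay.* That comparison supports only the survey exclusion.
- *That universal screening must run far more tests.* The threefold ratio needs equal uptake and only one third tested under targeted screening.
- *That positivity outside the targeted third can be back-calculated to size the effect.* Section 5.2 does not pair its two ranges (4-10% overall, 10-14% targeted). Pairing 4% with 12% gives (4 − 4)/(2/3) = 0%, and 4% with 14% gives (4 − 4.67)/(2/3) = −1%, which is impossible. Any workable pair would be a choice.

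**Conclusion.** The point holds in a limited, conditional form. The stated reasons do not justify setting collection labour to zero. If the unit test cost excludes that labour, and universal screening runs more tests and finds more cases, the universal-versus-targeted ICER and the prevalence threshold are both understated.

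The direction is clear under those conditions; the size is not. The reference range of $250-1,333 per extra case rests on assumed labour of $3.75-10 per test, one third tested under targeted screening, full uptake in both strategies and no urine already ordered. Relaxing the last three lowers the figure, to zero in some uptake patterns. A reader might infer that the prevalence threshold is materially wrong, but the documents give no test cost or QALY value from which to show that. The change is worth making because it is cheap and the present plan has no way to find out. Confidence is moderate.

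**What to change.** In Section 5.1, replace the sample-time exclusion with the following:

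1. State what the unit cost of a GC/CT test contains.
2. If it does not contain collection labour, add a per-test labour cost (minutes × wage), charged only where no urine was already ordered.
3. Give this parameter a range that includes 0, which is the present assumption, and vary it in the deterministic and probabilistic sensitivity analyses.
4. Report the ICER and the prevalence threshold with and without it.
5. Add tablet and survey staff time only for comparisons with usual care.

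The cost is SAP wording and one or two model parameters, with no change to trial conduct. The workflow observations may supply some collection timings, but they come before the tablets are deployed and will not cover hand-out, so the minutes will be largely assumed and should be labelled so. Universal screening's ICER becomes somewhat less favourable.

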3.5 Cost-effectiveness analysis

Even if clinical strategies, such as universally offered screening for STIs, are proven to be effective, the costs of those strategies compared with usual care or more targeted approaches may make them impractical and unsustainable in a cost-constrained healthcare system. Cost-effectiveness analysis is a commonly used tool that allows policy makers and clinicians to measure the benefits gained for the additional costs of such strategies. The result of a cost-effectiveness analysis is the incremental cost-effectiveness ratio (ICER), which describes the additional cost of the more expensive but more effective strategy being examined, in this case universally offered STI screening, compared with the lesser cost of the less effective strategy (we have hypothesized this will be targeted screening) divided by the measure of effectiveness being considered. The most commonly used metrics in the peer-reviewed medical literature examine the incremental cost per quality-adjusted life year (QALY) gained; however, any meaningful measure of effectiveness can be used. For this project, we plan to look at additional cost per STI detected, as well as cost per QALY gained. We will develop decision analytic models (using Markov state transition structure) to evaluate the cost-effectiveness of universally offered screening compared

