5.2 Sample Size Calculations and Statistical Power

Workflow Analyses: We estimate that we will observe between 20-30 individuals per site, which is a common sample size for studies of ED workflow processes.

Difference	Power
0.5%	80%
0.75%	98%
1%	99%

Table 2: Power Calculations

Pragmatic Trial: We plan to enroll at 6 PECARN sites. Based on PECARN data, with 6 sites for 52 two-week periods, we conservatively anticipate that approximately 288 patients or more per two weeks per site will arrive. Of these, we conservatively expect to enroll 242 per site. About 220 of these will be asymptomatic and included in the primary analysis. Our preliminary data reveal STI screening rates of 0.16% (usual care) leading to detection rates less than 0.02%. Asymptomatic STI detection rates range from 4-10% in a population of universally offered screening. In a targeted population, which makes up about 1/3 of the overall asymptomatic population, 10-14% will test positive. This leads to estimated detection rates of approximately 3-5%. For power calculations, we assume a detection rate of 4.5% using a targeted strategy and a standard deviation in rates across sites of 2%. Based on expected enrollment of 220 asymptomatic patients per time period per site, we will have approximately 99% power to detect a 1% difference in detection rates, and over 80% power to detect a difference as small as 0.5% between targeted and universally offered strategies (see table above). A 1% difference in detection corresponds to approximately 450 additional STIs detected per year at these sites alone. If results from this study inform screening at centers across the country, the numbers captured could be orders of magnitude higher. Additionally, we will also have adequate power for subgroup analyses based on gender, age, race/ethnicity, and symptomatology, as the design will provide over 90% power to show a difference in detection rates of 2% for subgroups as small as 40 patients per month. Confidence intervals around detection rates in each of the screening strategy groups will be smaller than +/- 0.3%.

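### Section 5.1 calls the risk-tool cut point with the lowest ICER optimal, but a lowest ratio ignores how much benefit is gained (optional analysis, low severity)

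*Combined protocol and SAP*

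**What the plan says.** The cost-effectiveness part of section 5.1 says the team will be able to try several cut points for the risk tool "to see if there is an optimal cut point that minimizes the incremental cost-effectiveness ratio", and glosses this as "finding the best balance between sensitivity and specificity for the risk prediction tool". The wording is permissive.

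Section 5.1 does not say which two options the ICER compares, or which effect measure it uses. Section 3.5 describes the ICER in general as "the additional cost of the more expensive but more effective strategy being examined, in this case universally offered STI screening", set against targeted screening, and on effect measures says "we plan to look at additional cost per STI detected, as well as cost per QALY gained". Neither is assigned to the cut points.

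On costs, section 5.1 states that "time to complete survey will not be entered into the model" and also leaves out the time to obtain samples. Section 3.5 says of the costs: "These will include current and future costs related to both the intervention and downstream events related to treated or missed STIs". It lists no fixed per-patient item.

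The only willingness-to-pay level, $50,000/QALY in section 3.5, serves another purpose: "We will calculate the threshold of background STI prevalence above which universally offered screening becomes very cost-effective". The acceptability curves in section 5.1 concern the winning strategy and are not tied to cut points.

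**The concern.** Choosing among mutually exclusive options by the lowest ICER is not a cost-effectiveness decision rule. The ratio discards the amount of benefit, and minimising it never uses willingness to pay, so the same cut point comes out as optimal whatever a QALY is worth. None of the available readings repairs this:

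- **Each cut point against usual care.** With little fixed cost, the rule favours the stratum with the highest positivity. The pick also shifts with any fixed cost per patient.
- **Universal over targeted, as in section 3.5.** The rule favours whichever targeted cut point makes universal screening look best. The team may not intend this reading.
- **Sequential ICERs along an efficiency frontier.** These rise from step to step, so the lowest is always the first step.

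The rule can therefore label as optimal a cut point that forgoes gains costing less than $50,000/QALY. It also gives missed cases no weight of their own, so it need not deliver the sensitivity/specificity trade-off that section 5.1 gives as its purpose.

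**Working it through.** The plan states no ICER, cut-point value, sensitivity or specificity, so there is no figure of its own to reproduce. The check is an illustration.

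**Inputs from section 5.2.** "In a targeted population, which makes up about 1/3 of the overall asymptomatic population, 10-14% will test positive". As a consistency check, 1/3 x 10-14% = 3.3-4.7%, in line with the plan's targeted detection rate of approximately 3-5%. Universal detection is given as 4-10%.

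**Assumed.** Half the targeted third has 14% positivity (narrow cut point N tests only these). The other half has 10% (broad cut point B adds them). Universal screening (U) detects one point more than B, i.e. 5.0%. Everyone selected is tested, the test is perfect, there is no fixed cost, and cost is counted in tests.

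**Per patient**

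| | Tested | Cases |
|---|---|---|
| N | 1/2 x 1/3 = 0.1667 | 0.1667 x 0.14 = 0.0233 |
| B | 0.3333 | 0.0233 + 0.1667 x 0.10 = 0.0400 |
| U | 1 | 0.0500 |

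**Tests per case**

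- Against no screening: N 0.1667/0.0233 = 7.1; B 0.3333/0.0400 = 8.3. Netting off usual care (0.16% screened, 0.02% detected) leaves both at 7.1 and 8.3.
- Universal over targeted: over N, 0.8333/0.0267 = 31.3; over B, 0.6667/0.0100 = 66.7.
- B over N: 0.1667/0.01667 = 10.0.

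Both comparators pick N, although B finds 1.67 more cases per 100 patients at 10 tests each.

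**Sensitivity/specificity.** Sensitivity = cases/0.05; specificity = 1 - (tested - cases)/0.95.

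- N: 0.467 and 1 - 0.1433/0.95 = 0.849; sum minus 1 = 0.32.
- B: 0.800 and 1 - 0.2933/0.95 = 0.691; sum minus 1 = 0.49.

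B stays ahead on this index when the 14% half becomes 25% of the targeted group (0.17 against 0.47) or 75% (0.43 against 0.51). In these two runs U is kept one point above B, at 4.67% and 5.33%. With the 50/50 split, B also stays ahead at universal detection of 4.5% (0.37 against 0.58) and 8% (0.14 against 0.18). At 10% the two tie at 0.07.

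**Fixed cost per patient, F, against usual care.** The pick switches to B where (F + 0.1667)/0.0233 = (F + 0.3333)/0.0400, so F = 0.067 test costs. For shares of 25% and 75% it is 0.033 and 0.100. Under universal over targeted, a survey cost common to both strategies cancels, because section 4.1 has patients complete the survey in both. The 31.3 and 66.7 then do not move.

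**Rerun at the plan's 4.5% targeted rate.** Mean positivity is 0.045/(1/3) = 13.5%, split (assumed) as 18% and 9%, with U at 5.5%. Cases are N 0.0300, B 0.0450, U 0.0550. Tests per case are 5.6 against 7.4 versus no screening, and 33.3 against 66.7 for universal over targeted. B adds 1.5 cases per 100 at 11.1 tests each. The switch is at F = 0.167, and the index is 0.40 against 0.51.

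**Net monetary benefit.** With cost c per test, q QALYs per detected case and $50,000/QALY, B exceeds N when 50,000 x q x 0.01667 > c x 0.1667, i.e. q > 10c/50,000. For assumed c of $20, $50 and $100 this is 0.004, 0.010 and 0.020 QALY. Below that, N has the higher net benefit and the two rules agree. Treatment, false positives and averted sequelae are not counted.

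**Second check, all inputs assumed except the prevalence range and $50,000/QALY.** This uses a continuous normal risk score with separation 1, $50 per test, $100 per false positive, test sensitivity 95% and specificity 99.5%. Prevalence was 4-10%, fixed cost $0-5 and gain 0.02-0.05 QALY per case. In all 18 scenarios the lowest-ICER cut point differed from both the maximum-net-benefit one and the one maximising sensitivity plus specificity. Its sensitivity ran from about 0 to 0.45, against 0.58 to 0.98 for maximum net benefit.

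**The case against.** The strongest reply is that little depends on this and that the example is favourable to the criticism.

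- **Materiality.** The clause is permissive and sits within the sensitivity analyses. This stands, and it is why severity is low.
- **Fixed cost.** The base case sets it to zero, while section 3.5 includes intervention costs and every participant completes a tablet survey, so some cost per patient is plausible. Against usual care the switch at 0.067 test costs is only $1.33-$6.67 at $20-$100 per test ($3.33-$16.67 in the 4.5% rerun). Above it, the lowest ICER picks B, the index picks B, and net benefit picks B whenever either cut point is worth using, because B's ratio then exceeds the 10 tests of the step from N. This also stands: in that range the plan's equation holds in this example. But the agreement then rests on a cost that the plan does not itemise and a comparator that it does not name.
- **Metric.** Sensitivity plus specificity minus 1 is not in the plan, and a balance could be weighted by the costs of errors, which section 3.5 will model. That is fair, but a cost-weighted balance is in effect net benefit, not a minimum ratio.
- **Continuous score.** Section 4.1 describes three risk categories, so few real cut points exist. The second check does not show that the error is likely for this tool.
- **Threshold.** Section 3.5 uses $50,000/QALY only for the prevalence question. The fix should therefore use a range of thresholds as well.

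**Conclusion.** The concern holds, at low severity. As written, the rule is wrong in principle: it can name a cut point that forgoes worthwhile gains, and it is not the same as a sensitivity/specificity trade-off. Confidence is high on the principle.

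The size in this trial is unknown. The numerical contrast rests on the assumed split of the targeted group, test costs and QALY gains. Against usual care it also needs a low fixed cost per patient and a gain per detected case above the break-even.

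Only the label attached to a cut point in an optional modelling analysis is affected. Hypotheses 2a and 2b, the three-strategy comparison and the prevalence threshold do not use it. Section 3.5 does expect the modelling to inform screening policy, so a published optimum could be taken up. Nothing here says which cut point should be used in practice.

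**What to change.** In section 5.1, replace minimising the ICER with selection by maximum expected net monetary benefit at $50,000/QALY (the level in section 3.5) and at a range of other thresholds. Equivalently, place all cut points, usual care and universal screening on one efficiency frontier and report sequential ICERs after removing dominated options. For cost per STI detected, where no threshold is stated, report the sequential ratios without naming the smallest as optimal. Show sensitivity and specificity for each cut point beside its net benefit.

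The cost is one or two sentences in the plan. The same model runs supply the numbers.
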